[Part 2 of 4 of the document. The other parts are not shown.]

Compliance with this request for prompt reporting is essential in that the sponsor is responsible for informing the US Food and Drug Administration (FDA) and other regulatory authorities as well as all other participating Investigators of the event.

Under FDA ruling (US Code of Federal Regulations, Title 21 CFR Part 312.32) and the ICH Guidelines for Clinical Safety Data Management Definitions and Standards for Expedited Reporting, the sponsor is required to submit written documentation, in the form of a safety report, detailing:

- Any event associated with the use of the drug, that is both serious and unexpected, or
- Any finding from tests in laboratory animals that suggests a significant risk for human subjects, including reports of mutagenicity, teratogenicity, or carcinogenicity.

Written submission must be made by the sponsor to the FDA and the IRBs as soon as possible and in no event later than 15 calendar days after the sponsor's initial notification of the event. The sponsor shall also inform all Investigators.

**11.3.9.2 Time Frame for Reporting**

Any death, SAE, pregnancy, or unexpected (and severe) AE experienced by the subject after informed consent or within 28 days of receiving study drug, regardless of relationship to study drug, or any death that occurs more than 28 days after receiving study drug, and is believed to be study drug related, must be promptly reported (within 24 hours of the Investigator becoming aware of the event) by telephone or electronic transmission to the sponsor (or designee).

Contact information for SAE reporting:

Medpace Clinical Safety  
Medpace SAE hotline:  
Telephone: PPD [redacted] dial P or PPD [redacted] dial P  
Facsimile: PPD [redacted] or PPD [redacted] D  
e-mail: PPD [redacted]

Additionally, the Investigator will be able to contact the **Medical Monitor**:

### 11.3.9.3 Information to be Provided by the Investigator

SAEs must be recorded on the SAE form in the EDC system. This requirement includes all SAEs that occur after informed consent and through 28 days after study drug dosing, and in addition, any SAE that are assessed as related to study treatment by the Investigator, even if the SAE occurs more than 28 days after study drug dosing.

The minimum information required for SAE reporting includes identity of Investigator, site number, subject number, an event description, SAE term(s), onset date, the reason why the event is serious (i.e., the seriousness criteria) and the Investigator's assessment of the relationship of the event to study treatment. Additional SAE information including medications or other therapeutic measures used to treat the event, action taken with the study treatment due to the event, and the outcome/resolution of the event will be recorded. Paper forms for reporting SAEs will be provided to the study sites as back-up in case the EDC system is not accessible.

In all cases, the Investigator should continue to monitor the clinical situation and report all material facts relating to the progression or outcome of the SAE. Furthermore, the Investigator may be required to provide supplementary information as requested by Syntimmune or designee.

When reporting an SAE, the following additional points should be noted:

- When the diagnosis of an SAE is known or suspected, the Investigator should report the diagnosis or syndrome as the primary SAE term, rather than as signs or symptoms. Signs and symptoms may then be described in the event description. For example, dyspnea should not be used as an SAE term if the diagnosis, which caused the dyspnea, is known to be malignant pleural effusion.
- Death should not be reported as an SAE, but as an outcome of a specific SAE, unless the event preceding the death is unknown. In the exceptional case where the events leading to death are unknown, then death may be used as an event term. If an autopsy was performed, the autopsy report should be provided.
- While most hospitalizations necessitate reporting of an SAE, some hospitalizations do not require SAE reporting, as follows:
  - Elective or previously scheduled surgery, e.g., a previously scheduled ventral hernia repair
  - Procedures for pre-existing conditions that have not worsened after initiation of treatment
  - Pre-specified study hospitalizations for observation
  - Events that result in hospital stays of less than 24 hours and that do not require admission, e.g., an emergency room visit for hematuria that results in a diagnosis of cystitis and discharge to home on oral antibiotics
- SAEs must, however, be reported for any surgical or procedural complication resulting in prolongation of the hospitalization.

#### **11.3.10 Regulatory Reporting**

Syntimmune (or designee) will process and evaluate all SAEs as soon as the reports are received. For each SAE received, Syntimmune will decide as to whether the criteria for expedited reporting have been met.

Syntimmune (or designee) will submit SAEs that meet the criteria for expedited reporting to the regulatory authorities in accordance with local regulations governing safety reporting. Reporting of SAEs by the Investigator to his or her IRB will be done in accordance with the standard operating procedures and policies of the IRB. Adequate documentation must be maintained showing that the IRB was properly notified.

### **11.3.11 Follow-up Information on a Serious Adverse Event (SAE)**

Appropriate diagnostic tests should be performed and therapeutic measures, if indicated, should be instituted. Appropriate consultation and follow-up evaluations should be carried out until the event has returned to baseline or is otherwise explained by the Investigator.

If all required information on the SAE form is not available at the time of the initial report, follow-up information will be completed in the EDC system.

## **11.4 Other Safety Considerations**

### **11.4.1 Laboratory Data**

All laboratory data obtained during the study should be reviewed. Any abnormal value that leads to a change in subject management (e.g., requirement for additional medication or monitoring) or is of clinical significance by the Investigator should be reported as an AE and/or SAE as appropriate, unless this value is consistent with values obtained before entry into the study.

### **11.4.2 Medication Errors**

Any medication error that results in an AE, even if it does not meet the definition of serious, requires reporting within 24 hours to the safety Medical Monitor.

### **11.4.3 Follow-Up of Adverse Events**

Any SAE or AE assessed as related that led to treatment discontinuation (including clinically significant abnormal laboratory values that meet these criteria) and ongoing 28 days after study drug dosing must be followed until either resolution of the event or determination by the Investigator that the event has become stable or irreversible. This follow-up guidance also applies to related SAE that occur more than 28 days after study drug dosing. The status of all other continuing AEs will be documented as of 28 days after study drug dosing. The Investigator will follow all subjects who experience AEs until there is a return to the subject's baseline condition, or until a clinically satisfactory resolution has been achieved. The appropriate follow-up visits must be scheduled and the specific tests repeated or performed as necessary.

Where a diagnosis is possible, it is preferable to report this diagnosis rather than a series of terms (signs/symptoms) relating to the diagnosis.

### **11.5 Safety Monitoring for Dose Escalation**

Following dosing in each cohort, all safety/tolerability data (e.g., PEs, vital signs [including pulse oximetry], clinical safety laboratory tests, ECGs and AE/SAE assessments) as well as any available and relevant PD data collected through Day 42 will be reviewed by the DEC. A decision to escalate to the next cohort will be made. The recommendation may be to continue to the next scheduled dose level, discontinue the study or to modify dosing to a dose less than the current dose or higher than the current dose but lower than the next planned dose.

## 12 STATISTICAL CONSIDERATIONS

All descriptive and inferential statistical analyses will be performed using the most recently released and available Statistical Analysis System (SAS) software, unless otherwise noted. Missing data will not be imputed unless otherwise stated. All clinical data captured will be provided in data listings. A Statistical Analysis Plan (SAP) and a Pharmacokinetic Analysis Plan (PAP) will be finalized prior to database lock.

### 12.1 General Design

All data for enrolled subjects will be presented in data listings by subject number.

Continuous data will be described using descriptive statistics: number of observations (n), mean, standard deviation (SD), median, minimum, and maximum. Frequencies and percentages will be used for summarizing discrete (categorical) data. When categorical data are presented, the percent will be suppressed when the count is zero to draw attention to the non-zero counts. The denominator for all percentages, unless otherwise specified, will be the number of subjects in the specified analysis population.

### 12.2 Sample Size Justification

Formal sample size calculations were not performed. The number of subjects was chosen based on feasibility and was considered sufficient to meet the study objectives.

### 12.3 Statistical Considerations

Detailed methodology for summary and statistical analyses of the data collected in this study will be documented in a statistical analysis plan (SAP). The SAP may modify the plans outlined in the protocol; any deviations from the previously described statistical plan will be described and justified in an SAP amendment. Additional statistical analyses other than those described in this section may be performed if deemed appropriate and will be described in the SAP. Methods of handling of missing data for different endpoints will be further specified in the SAP. In general, where individual data points are missing because of insufficient samples, dropouts, or other reasons, the data will be analyzed based on reduced denominators unless specified otherwise in the SAP.

Results will be summarized by cohorts.

#### 12.3.1 Study Populations

Three populations will be employed in the analysis of study data:

- The **intent-to-treat (ITT)** population will consist of all subjects who have received at least one dose of study drug. All safety analyses will be performed on the ITT population.
- The **PK** population will consist of all subjects who receive at least one dose of study drug and have sufficient post-dose blood samples to obtain PK parameters.
- The **PD** population will consist of all subjects who receive at least one dose of study drug and have post-dose PD data available.

Primary safety analyses will be performed on the ITT population. Demographics, subject disposition, and screening and baseline characteristics will be summarized for the ITT, PK, and PD populations, where appropriate.

### **12.3.2 Subject Accountability, Demographics, and Baseline Characteristics**

Subject disposition, demographic information and baseline characteristics will be presented. Any discrepancy between treatment to be given and treatment received will be accounted for in these displays.

### **12.3.3 Concomitant Medications**

Concomitant medications will be coded using WHO Drug Dictionary (WHO-DD March 2013, Type B2 or later) and the data will be summarized and presented in tables and listings.

## **12.4 Planned PK Analysis**

Study drug concentrations will be used to calculate the following PK parameters:  $t_{1/2}$ ,  $C_{max}$ ,  $T_{max}$ , and  $AUC_{0-24}$  and  $AUC_{0-\infty}$ . PK parameters will be determined using noncompartmental method(s). Descriptive statistics of PK parameters for SYNT001 will include mean, SD, coefficient of variation (CV), median, minimum, and maximum.  $T_{max}$  will be reported as median and range. All descriptive statistics will be performed on untransformed PK parameters and after  $\log_{10}$  transformation of PK parameters.

For calculation of mean concentrations and generation of mean concentration-time profiles, all below the limit of quantification (BLQ) values will be set to zero except when an individual BLQ falls between 2 quantifiable values, in which case it will be omitted.

If there are values above the BLQ, but too sparse to allow full analysis, descriptive statistics will be performed on available values.

## **12.5 Safety Data**

Safety observations and measurements include AEs, safety laboratory tests, vital sign measurements, PEs, and ECGs.

Treatment-emergent AEs will be summarized using the Medical Dictionary for Regulatory Activities (MedDRA®; Version 19 or higher) System Organ Class (SOC) and preferred term, classified from verbatim terms. The incidence and percentage of subjects with at least 1 occurrence of a preferred term will be included, using the most severe grade. The number of events per preferred term will also be summarized. Causality (relationship to study treatment) will be summarized separately.

AEs, SAEs, and AEs leading to withdrawal, dose modification, or treatment discontinuation will be listed by subject, cohort, and overall per SOC and preferred terms. Duration of AEs will be determined and included in listings, along with action taken and outcome.

Laboratory results will be summarized by cohort. Incidence of laboratory abnormalities will be summarized. The worst on-study grade after the first dose of study drug will be summarized. Results for variables that are not coded will be presented in the listings as below, within, and above the normal limits of the local laboratory.

Vital sign measurements and change from baseline will be summarized at each scheduled time point by cohort using descriptive statistics.

Arithmetic mean of parameters from triplicate ECG will be calculated first for each participant at each planned time point. Then summary statistics of ECG test parameters (mean of triplicate) and change from baseline to each post-dose time point will be calculated. Shift tables for ECG test result category change (normal, abnormal, clinically abnormal) from pre-dose to each post-dose time point showing number and percentage of subjects with movement between categories will be presented by treatment group. Frequency and percentage of subjects experiencing potential QTc prolongation ( $QTcF > 450$ ) will be summarized at each time point by cohort.

## **12.6 Pharmacodynamic/Activity Data**

PD results will be summarized by cohort.

## **12.7 Immunogenicity Data**

Immunogenicity results will be summarized by cohort.

## **12.8 Interim Analysis**

No interim analysis is planned. Safety results will be examined for making dose-escalation decisions; no statistical analyses are planned for aiding these dose-escalation decisions.

### 13 DATA QUALITY ASSURANCE

All data will be entered in a validated electronic data capture system using single data entry. Standard procedures (including following data review guidelines, manual clinical review based on subject profiles, computerized validation to produce queries, and maintenance of an audit file which includes all database modifications) will be followed to ensure accurate data. Clinical personnel will review all data listings for outliers, data inconsistencies, and spelling errors.

During the study, a study site monitor will make site visits to review protocol compliance, compare electronic case report forms (eCRFs) against individual subject medical records, assess drug accountability, and ensure that the study is being conducted using pertinent regulatory requirements. eCRF entries will be verified with source documentation. The review of medical records will be performed in a manner to ensure that subject confidentiality is maintained. Checking the eCRFs for completeness, clarity and cross checking with source documents is required to monitor the progress of the study. Direct access to source data is also required for inspections and audits, and will be carried out giving due consideration to data protection and medical confidentiality. Each Investigator will have assured Syntimmune of full access to complete source data for study participants and associated necessary support at all times.

In addition to routine monitoring procedures, audits of clinical research activities in accordance with standard operating procedures (SOPs) may be performed to evaluate compliance with the principles of GCP. A regulatory authority may also wish to conduct an inspection (during the study or even after its completion). If a regulatory authority requests an inspection, the Investigator must immediately inform Syntimmune that this request has been made. Study conduct may be assessed during the study by a Clinical Quality Assurance representative(s) to ensure that the study is conducted in compliance with the protocol. This designee, as well as the site monitor, will be permitted to inspect the study documents (study protocol, eCRFs, investigational product accountability, original study-relevant medical records). All subject data will be treated confidentially. During the clinical study, access will be available to Syntimmune or their designee (e.g., contract research organization [CRO]) to view the eCRFs after completion of the individual sections of the study. Furthermore, the study protocol, each step of the data-recording procedure and the handling of the data as well as the study report may be subject to independent review by a Quality Assurance representative. Clinical site and study audits will be conducted as necessary to assure the validity of the study data.

---

## 14 STUDY ADMINISTRATION

### 14.1 Study Administrative Structure

The study administration structure is provided in Table 6.

### 14.2 Ethical Conduct of the Study

The study must fully adhere to the principles outlined in “Guideline for Good Clinical Practice” ICH E6 Tripartite Guideline (January 1997), and in general, be conducted in a manner consistent with the principles described in the Declaration of Helsinki. The Investigator will ensure that the conduct of the study complies with the basic principles of GCP as outlined in the current version of 21 CFR, subpart D, Part 312, “Responsibilities of Sponsors and Investigators”, Part 50, “Protection of Human Subjects”, and Part 56, “Institutional Review Boards”.

### 14.3 Informed Consent (ICF)

A properly executed, written informed consent document, in compliance with 21 CFR, Part 50 and the ICH guidelines, will be obtained from each subject before the subject is entered into the study and before any study screening procedure is performed that involves risk. Attention will

be directed to the basic elements required for incorporation into the informed consent under US Federal Regulations for Protection of Human Subjects (21 CFR 50.25[a]) and (21 CFR 50.25[b]), as necessary.

Sample ICFs will be supplied to each site. Syntimmune or its designee must review any proposed deviations from the sample ICF. The final IRB-approved document must be provided to Syntimmune for regulatory purposes.

It is the responsibility of the Investigator, or a person designated by the Investigator, to obtain written informed consent from each subject (or the subject's legally authorized representative) participating in this study after adequate explanation of the aims, methods, anticipated benefits, and potential hazards of the study. In the case where the subject is unable to read, an impartial witness should be present during the entire informed consent discussion. After the subject has orally consented to participation in the trial, the witness' signature on the form will attest that the information in the consent form was accurately explained and understood. A copy of the ICF must be provided to the subject or to the subject's legally authorized representative. If applicable, it will be provided in a certified translation of the local language.

The eCRF for this study contains a section for documenting informed subject consent, and this must be completed appropriately. Signed ICFs must remain in each subject's study file and must be available for verification by site monitors at any time. If new safety information results in significant changes in the risk/benefit assessment, the consent form should be reviewed and updated as necessary. All subjects (including those already being treated) should be informed of the new information, should be given a copy of the revised form, and should give their consent to continue in the study.

#### **14.4 Institutional Review Board**

This study is being conducted under US IND 128152. This protocol (and any modifications) and appropriate consent procedures must be reviewed and approved by an IRB. This board must operate in accordance with the current federal or local regulations. The Investigator will send a letter or certificate of IRB approval to Syntimmune (or designee) before subject enrollment and whenever subsequent modifications to the protocol are made.

#### **14.5 Dose Escalation Committee**

The DEC will be responsible for confirming the safety of the investigative product prior to dose escalation, as well as the dose level for each successive cohort. In addition, over the course

of the study, the DEC will review any drug-related SAEs to determine if modifications to the study or other measures are necessary to ensure the safety of the subjects. The DEC will consist of the Medical Monitor, an Independent Clinical Expert and a Syntimmune Medical Officer. To assist in the safety assessments, the DEC may request that Investigators, other experts, or members within their organizations review the data and participate in the discussions.

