Safety evaluations will be conducted by a dose escalation committee (DEC). The DEC will consist of the Medical Monitor, an Independent Clinical Expert and a Syntimmune Medical Officer. To assist in the safety assessments, the DEC may request that Investigators, other experts, or members within their organizations review the data and participate in the discussions. Dosing and dose escalation will proceed if the DEC has determined that it would be safe and appropriate to do so. In addition, over the course of the study, the DEC will review any drug-related SAEs to determine if modifications to the study or other measures are necessary to ensure the safety of the subjects.

On days where study drug is administered, vital sign and pulse oximetry measurements will be collected immediately prior to the infusion; 15, 30, and 45 minutes after the start of the infusion; at completion of the infusion; and 30 minutes, 1 hour and 2 hours following completion of the infusion.

On Days 0 and 28, PK blood samples will be collected prior to infusion start and then over the subsequent 48 hours. Subjects will remain at the clinic through the 6-hour PK sample collection and will return to the clinic for the 24- and 48-hour collections. Additional samples will be collected on Days 5 and 33.

On Day 0 photographs will be taken of active lesions. Follow-up photographs will be taken of the same areas on Days 33, 56, 84, and 112. If a subject begins a steroid taper, additional photographs will be taken at the clinic visit during which the decision to begin the taper is made.

Subsequent visits will occur on Days 1, 2, 5, 7, 12, 14, 19, 21, 28, 29, 30, 33, 42 and 56 for safety assessments, study drug dosing, sample collections, and other study procedures.

Subjects also will return to the clinic on Days 84 and 112 for follow-up visits. Subjects whose total IgG is not within 30% of their Day 0 baseline value and not above 500 mg/dL at the Day 112 visit will be referred for further management.

See [Table 1](#) for a schedule of all study events. To assess safety and tolerability, subjects will undergo physical examinations (PEs; including weight), vital sign measurements, clinical (safety) laboratory tests, AE assessments, concomitant medication assessments, and electrocardiograms (ECG).

**Note:** No vaccinations may be given from within 2 weeks of screening through Day 56. Following Day 56, subjects may receive vaccinations at the discretion of the Investigator.

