## 10 CONCOMITANT MEDICATION AND TREATMENT

All treatments a subject receives within 14 days prior to enrollment through the end of the study will be documented. Concomitant medication and treatment for co-existing conditions, including those for pemphigus, are permitted if not excluded below. Topical antibiotics are permitted to treat active infections that occur on study. Topical or systemic treatments for oral candidiasis are permitted. Topical lidocaine for transient pain relief is acceptable as needed. Significant increases in anti-pemphigus medications will result in subjects being discontinued from the study. Concomitant treatment that is medically indicated for any AEs the subject experiences during the study are permitted. Premedication is discouraged as prophylaxis against AEs or infusion reactions unless medically indicated from either past medical history, prior infusion reactions or AEs resulting from SYNT001 infusions.

Use of the following treatments will not be permitted during the study unless otherwise specified:

- Rituximab or other anti-CD20 antibody
- Monoclonal antibodies other than study drug
- Any immunosuppressive drugs apart from corticosteroids, azathioprine, mycophenolate mofetil, or cyclosporine.
- Topical steroids
- Any dietary herbal supplements
- Any investigational drug or device
- Any vaccinations through Day 56. Following Day 56, subjects may be vaccinated at the discretion of the Investigator.

If over a period of at least two weeks on study drug, a subject on corticosteroids shows the absence of new lesions and significant healing of lesions that existed at study baseline, a slow corticosteroid taper may be started as per the following suggested schedule

- If on > 30 mg of prednisone per day, decrease by 10 mg every two weeks until a dose of 30 mg per day then decrease by 5 mg every two weeks
- If on < 30 mg of prednisone per day, decrease by 5 mg every two weeks

In cases in which concomitant medications are used, details to be recorded include the following: medication name, start date and time, stop date and time, dose, route, frequency, and reason for use. The concomitant medication names are to be coded using the World Health Organization (WHO) Drug Dictionary (WHO-DD March 2013, Type B2 or later) and classified by anatomical therapeutic chemical (ATC) categories.

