### 11.3.5 Assessment of Causality

A medically qualified Investigator must assess the relationship of any AE (including SAEs) to the use of the investigational product, as related or not related, based on clinical judgment and using all available information, and may include consideration of the following factors:

- Possible alternative causes of the AE, including the disease under treatment, pre-existing conditions, concomitant use of other drugs, and presence of environmental or genetic factors.
- The temporal association between drug exposure and onset of the AE.
- Whether the manifestations of the AE are consistent with known actions or toxicity of the investigational product.
- The AE resolved or improved with decreasing the dose or stopping use of the investigational product (dechallenge). Judgment should be used if multiple products are discontinued at the same time.

The causal relationship between the study medication and the AE will be assessed using one of the following categories:

**Not Related:** Factors consistent with an assessment of Not Related include:

- Temporal relationship is lacking (e.g., the event did not occur within a reasonable time frame following administration of the study medication); or
- Other causative factors more likely explain the event (e.g., a pre-existing condition, other concomitant treatments).

**Related:** Factors consistent with an assessment of Related include:

- There is a positive temporal relationship (e.g., the event occurred within a reasonable time frame following administration of study medication); or
- The AE is more likely explained by the investigational product than by another cause (i.e., the AE shows a pattern consistent with previous knowledge of the investigational product or the class of the investigational product)

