## **11.5 Safety Monitoring for Dose Escalation**

Following dosing in each cohort, all safety/tolerability data (e.g., PEs, vital signs [including pulse oximetry], clinical safety laboratory tests, ECGs and AE/SAE assessments) as well as any available and relevant PD data collected through Day 42 will be reviewed by the DEC. A decision to escalate to the next cohort will be made. The recommendation may be to continue to

the next scheduled dose level, discontinue the study or to modify dosing to a dose less than the current dose or higher than the current dose but lower than the next planned dose.

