#### **14.5 Dose Escalation Committee**

The DEC will be responsible for confirming the safety of the investigative product prior to dose escalation, as well as the dose level for each successive cohort. In addition, over the course of the study, the DEC will review any drug-related SAEs to determine if modifications to the study or other measures are necessary to ensure the safety of the subjects. The DEC will consist of the Medical Monitor, an Independent Clinical Expert and a Syntimmune Medical Officer. To

assist in the safety assessments, the DEC may request that Investigators, other experts, or members within their organizations review the data and participate in the discussions.

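### The Dose Escalation Committee's event-driven SAE review is limited to events the Investigator calls drug-related, so an SAE judged Not Related has no stated route to the committee's independent member between scheduled reviews

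*Protocol*

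**What the plan says.** The protocol file holds several versions; the wording below stands in the latest.

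- **Committee.** "The DEC will consist of the Medical Monitor, an Independent Clinical Expert and a Syntimmune Medical Officer" (Section 4.3). One of the three members is described as independent.
- **Event-driven remit.** Section 14.5 makes the DEC responsible for confirming safety before escalation and adds that "the DEC will review any drug-related SAEs to determine if modifications to the study or other measures are necessary to ensure the safety". Section 4.3 has the same restriction: "the DEC will review any drug-related SAEs".
- **Who decides relatedness.** "A medically qualified Investigator must assess the relationship of any AE (including SAEs) to the use of the investigational product" (Section 11.3.5). One listed ground for Not Related is "Other causative factors more likely explain the event (e.g., a pre-existing condition, other concomitant treatments").
- **Triggers.** The dose-escalation rule (Section 8.4.1, Grade 3 AEs in two or more subjects) and the study stopping rule (Section 8.4.2, any Grade 4 AE) both require the event to be considered related.
- **Scheduled review.** Under Section 11.5 all safety and tolerability data, together with "any available and relevant PD data collected through Day 42 will be reviewed by the DEC", whatever the causality label.
- **General statements.** Section 4.3 says that safety data are reviewed continuously through the study, naming no reviewer in that sentence, and then that the DEC conducts safety evaluations.
- **Reporting.** Every SAE goes to the sponsor or its designee within 24 hours regardless of relationship (Section 11.3.9.2), and the sponsor or designee evaluates it (Section 11.3.10). Neither section mentions the DEC.

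**The concern.** The hazard the protocol itself describes is infection while IgG is depleted, by up to 70% to 80% after multiple doses (Section 9.6.2). Section 10 bans "Any immunosuppressive drugs apart from corticosteroids, azathioprine, mycophenolate mofetil, or cyclosporine", so those four classes may continue as background therapy, and Section 5.2 admits subjects on corticosteroids up to 1 mg/kg/day of prednisone or equivalent. A serious infection in such a subject therefore has a ready alternative explanation that Section 11.3.5 accepts as a ground for Not Related.

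The trial is open-label and uncontrolled, and runs at about 10 sites. A handful of infections, each explained locally by background therapy, would show up only if someone looked across sites and ignored the local label. That is a natural job for the DEC and in particular for its independent member. A filter that depends on each Investigator's attribution works against it, and a pattern could build up while the rest of a cohort, or the next one, is being dosed.

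**Working it through.** The protocol states no statistical figure on this point. The check is to list every stated route by which an SAE could reach the DEC, and then to see which periods those routes leave open.

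**Step 1. Routes.**

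| Route | Section | Needs a Related label? | Period covered |
|---|---|---|---|
| Sentinel reviews | 4.3, 9.2 | No | 24 hours (subject 1); 7 days (first 2 subjects) |
| All-data cohort review | 4.3, 11.5 | No | Data through Day 42 |
| Decision on a third cohort | 4.3, 8.4.1 | No | Only if that cohort is considered |
| DEC review of SAEs | 4.3, 14.5 | Yes | Whole study |
| Grade 3 rule | 8.4.1 | Yes | Any time |
| Grade 4 rule | 8.4.2 | Yes | Any time |
| Continuous review | 4.3 | Not stated | Whole study, reviewer not named |
| SAE reporting and evaluation | 11.3.9.2, 11.3.10 | No | Whole study, but to the sponsor or designee |

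Every event-driven route that names the DEC requires relatedness. The routes that do not require it are scheduled reviews, go to the sponsor, or name no recipient.

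**Step 2. Can Section 4.3 be read so that the gap closes?** Suppose the sentence giving safety evaluations to the DEC means that it reviews all safety data continuously. The later sentence, which adds drug-related SAEs to its tasks, would then add nothing. Suppose instead that the first sentence refers to the sentinel and escalation evaluations described around it. SAEs judged Not Related are then unrouted between those evaluations. Section 14.5, which sets out the committee's responsibilities, contains only the escalation task and the drug-related task, and so fits the second reading. The text does not settle the matter.

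**Step 3. Periods left open on the second reading.**

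- *Before the cohort review.* Sentinel data cover 2 of 8 subjects, leaving 8 − 2 = 6. For those six, the open period runs from first dose to the cohort review, so for at least 42 days, and includes all five infusions (Days 0 to 28). For the first two subjects it begins at about Day 7.
- *After the cohort review.* Follow-up continues to Day 112 (Section 7.18) with no further all-data DEC review specified, except in support of a third cohort.

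**Step 4. How much of the later period carries the named hazard?** Inputs: last dose on Day 28 (Section 9.3); IgG expected back to within 30% of baseline within 4 weeks after multiple doses, from non-human primate data (Section 9.6.2); cut-off at Day 42 of the cohort's last subject (Section 4.3).

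- Expected recovery: 28 + 28 = Day 56.
- Expected low-IgG days after the cut-off, last subject: 56 − 42 = 14.
- A subject who started k days before the last one is at Day 42 + k at the cut-off, which leaves 14 − k such days, and none if k is 14 or more.

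**The case against.** The strongest reply is that the DEC's remit is wider than the SAE sentence. Section 4.3 describes the sentinel reviews and the continuous review and then gives safety evaluations to the DEC with no relatedness limit; the drug-related SAEs come in as an addition, not a cap. A reader might infer from Section 14.5 that, outside the Day 42 review, the DEC sees nothing but related SAEs, or that unrelated ones bypass it. The documents do not support that. SAEs up to the cohort cut-off appear in the all-data review whatever their label, a third cohort rests on all safety data, and the DEC may find at any time that the study should stop. What remains is that no sentence guarantees delivery of a Not Related SAE between those reviews.

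A reader might also take the 70 days from Day 42 to Day 112, or 70/112 = 62.5% of follow-up, as the size of the blind period. That fits only a cohort's last-dosed subject, because the cut-off is tied to that subject and others are already further on. Of those 70 days, about 14 carry expected low IgG.

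The causality criteria also work both ways. A plausible time relationship, or a pattern consistent with the drug, supports Related, so an infection near the IgG nadir could well be called Related. That is fair. It means that the label may differ between Investigators, not that it will usually be Not Related. The protocol gives no misattribution rate, so no probability of a missed event can be attached.

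Finally, the sponsor receives every SAE, and the Medical Monitor or the sponsor's Medical Officer may well see it and raise it. That softens the consequence, but it leaves the independent member's access to their discretion. The DEC is not presented as an independent monitoring board, and nothing here requires it to become one.

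**Conclusion.** The point holds in a limited form. The protocol states a restrictive rule for event-driven SAE review and pairs it with broader statements in Section 4.3 that do not match. The result is that an SAE judged Not Related has no stated route to the Independent Clinical Expert in two periods: between the sentinel reviews and the cohort review, and after the cohort review while the next cohort may be dosing. The second period includes at most about 14 days of expected low IgG, for a cohort's last subject. The first is the more exposed, because it spans the dosing of six of the eight subjects.

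This rests on three assumptions: that the protocol text at hand is complete on SAE routing and no committee charter sets a wider rule; that the 4-week IgG recovery seen in non-human primates carries over; and that the Day 42 cut-off follows the last subject, as Section 4.3 says for Cohort 1. The finding concerns what the committee receives. It does not show that any event would be missed, and it does not touch the stopping thresholds. It is a cheap improvement worth making, not a flaw that undermines the trial.

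**What to change.** In Sections 4.3 and 14.5, replace the reference to drug-related SAEs with *all SAEs, regardless of the Investigator's causality assessment*, and state that this applies through the last study visit of every cohort. In Section 4.3, name who carries out the continuous safety review and align that sentence with the revised remit. Dosing, stopping thresholds and subject care stay as they are.

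The cost is one phrase in two sections, one clarifying sentence, and a few more case reports for a three-person committee. The sponsor already receives these reports within 24 hours, and at most 27 subjects may be enrolled (Section 5.1).
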